7.6. Pregnancy

All pregnancies of women participating in the study and female partners of men participating in the study, if applicable that occur during the study, or within 14 days of completion of the study, are to be reported immediately to the physician identified in the Clinical Study Personnel Contact Information section of this protocol, and the investigator must provide the LSO with the pregnancy form. The process for reporting a pregnancy is the same as that for reporting a serious adverse event but using the pregnancy form (see Section 7.5.5.3).

Any female patient becoming pregnant during the study will discontinue treatment. All patients (or female partners of men participating in the study) who become pregnant will be monitored for the outcome of the pregnancy (including spontaneous or voluntary termination). If the pregnancy continues to term, the outcome (health of the infant up to 8 weeks of age), including details of birth and presence or absence of any birth defect, congenital abnormalities, or maternal and newborn complications, will be reported to the sponsor. Any complication of pregnancy during the study and any complication of pregnancy that the investigator becomes aware of after withdrawal from the study will be reported as an adverse event or serious adverse event, as appropriate.

If the pregnancy does not continue to term, 1 of the following actions will be taken:

- For a spontaneous abortion, report as a serious adverse event.
- For an elective abortion due to developmental anomalies, report as a serious adverse event.
- For an elective abortion **not** due to developmental anomalies, report on the pregnancy form; do not report as an adverse event.

7.7. Medication Error and Special Situations

Any administration of medication that is not in accordance with the study protocol should be reported on the CRF either as a violation, if it meets the violation criteria specified in the protocol or as a deviation, in the patients source documents, regardless of whether an adverse event occurs as a result. All instances of incorrect medication administration should be categorized on the CRF as “Non-Compliance to investigational medicinal product (IMP)”.

Types of medication errors and special situations:

1. Medication error: Any unintentional error in the prescribing, dispensing, or administration of a medicinal product while in the control of the healthcare professional, patient, or consumer.
2. Overdose: Administration of a quantity of a medicinal product given per administration or cumulatively which is above the maximum recommended dose according to the authorized product information. Clinical judgment should always be applied.
3. Misuse: Situations where the medicinal product is intentionally and inappropriately used not in accordance with the authorized product information.
4. Abuse: Persistent or sporadic, intentional excessive use of medicinal products which is accompanied by harmful physical or psychological effects.
5. Off-label use: Situations where a medicinal product is intentionally used for a medical purpose not in accordance with the authorized product information.
6. Occupational exposure: Exposure to a medicinal product, as a result of one’s professional or non-professional occupation.

7.8. Laboratory Procedures

Blood samples and urine specimens must be obtained at the appropriate visits. Non-fasting samples may be obtained. Any laboratory samples which are outside the normal range must be assigned one of the following codes:

NS – Not Clinically Significant: A clinically meaningless departure from the normal range.

LE – Laboratory Error: Due to a poor sample, instrument error, etc. (the value is not valid).

PA – Patient Abnormality: Although the value is outside the normal range, the value is normal for that particular patient.

CS – Clinically Significant: A clinically meaningful departure from the normal range or a clinically meaningful change in the parameter. All clinically significant values during the study are adverse events and must be entered on the “Clinically Significant Lab Values” page of the Case Report Form.

7.8.1. Urinalysis

- Protein
- pH
- Specific gravity
- Glucose
- Microscopic examination of sediment

7.8.2. Hematologic Tests

- WBC
- RBC
- Differential white blood cells
- Platelet count
- Hemoglobin
- Hematocrit

[figure not shown]
7.8.3. Serum Chemistries

[figure not shown]
- BUN
- Creatinine
- Aspartate aminotransferase (AST) or SGOT
- SGPT (ALT)
- Alkaline phosphatase

- Bilirubin
- Phosphorous
- Total protein
- Albumin
- Calcium
- Cholesterol / triglycerides
- Glucose
- Serum electrolytes (Na⁺, K⁺, Cl⁻, Bicarbonate)

7.9. Immunological Analyses

For patients who consent to the optional immunological analysis, blood samples will be collected at the Amendment 12 screening visit (month 240) and the investigator visit (month 252). There will be no additional immunological assessments under Amendment 13. Samples will be analyzed as follows:

8. STATISTICAL METHODS

Standard reporting and analysis procedures will be employed to present the safety profile of Copaxone[®] and its effect on the neurologic course of the disease.

8.1. Adverse Events

The total number and percent of patients reporting adverse events, across and by body system and event term, will be tabulated for all patients treated. The number of patients treated will serve as the denominator for incidence rate computation. Adverse events will also be summarized by maximum reported severity and relationship to treatment. Detailed data displays, narrative summaries, and copies of Case Report Forms will be provided for those patients who withdrew prematurely due to an adverse event or who dies.

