3. OBJECTIVES

This study will continue to provide information regarding the safety of administration of Copaxone[®] to a large number of patients. It will also provide information regarding the safety of Copaxone[®] administered for up to 26 years, or until the sponsor terminates the study, on approximately 60 patients who participated in the original double-blind study.

The objectives of this study are:

- To assess the long-term safety of Copaxone[®] in relapsing-remitting MS patients by the ongoing monitoring of
 - Clinical pathology (blood and urine)
 - Adverse reactions
- To evaluate the long-term neurologic course of the disease in the patients receiving Copaxone[®] by regular neurological examinations including:
 - Functional system evaluation
 - Kurtzke Expanded Disability Status score
 - Ambulation Index (AI)
- To evaluate the neurologic course of the disease in these patients by the monitoring of exacerbations.
- To evaluate the imaging course of the disease in these patients receiving Copaxone[®] by performing an MRI examination following 24 years of continuous Copaxone[®] therapy and comparing it to a previous scan obtained following 20 and 22 years of continuous Copaxone[®] therapy as well as to the neurologic course of the disease following 24 years of continuous therapy.

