7. CONDUCT OF STUDY

7.1. Schedule of Activities and Evaluations

All procedures, tests, and examinations required for the study extension visits are listed on the Schedule of Activities Flow Chart found in [Appendix A](#).

Screening visits through month 264 must have been completed to continue in the study extension. For the purposes of this amendment, the termination visit of Amendment 12 (month 264), will act as the screening visit for this amendment. Patients who have completed the termination visit and discontinued from the study under the Amendment 12 protocol may still continue in the extension study under Amendment 13; for these patients, the screening visit for Amendment 13 will be a separate visit to the termination visit of Amendment 12.

The study extension will involve 1 investigator visit (Section [7.1.3.2](#)) annually supplemented by 3 nurse coordinator telephone visits (Section [7.1.3.1](#)). This schedule will maintain contact with the patients on a quarterly basis, approximately every 90 days. The study extension period will end with the termination visit (Section [7.1.3.3](#) and Section [7.1.5](#)) following 26 years of continuous Copaxone[®] therapy.

In addition to MRIs performed at month 240, the optional MRI sub-study will involve 2 MRIs for active study patients at the annual investigator visit (month 252) or at an unscheduled visit around the time of the investigator visits and at the final investigator visit for Amendment 12/screening visit for Amendment 13 (month 264).

The optional immunological sub-study will involve 2 blood samples, 1 taken during the screening visit for Amendment 12, and 1 at the next treatment visit at month 252. There will be no additional immunological assessments under Amendment 13.

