7.1.1. Screening Visit for Amendment 13 (Month 264)

During screening for Amendment 13, the patient must be thoroughly informed about all aspects of the study extension, including the study visits and activities schedule. Written informed consent must be obtained.

At this visit, patients will be given the option of either continuing treatment with Copaxone 20 mg daily or switching to Copaxone 40 mg TIW. The choice of treatment will be recorded for each patient.

A checklist of the procedures to be performed during the screening visit follows.

- Eligibility checklist
- Signed informed consent for Amendment 13
- Record treatment (20 mg daily or 40 mg TIW)

- Complete neurological examination, including:
 - Functional Systems Status (FS) Evaluation ([Appendix D](#))
 - Kurtzke Expanded Disability Status Score (EDSS) ([Appendix C](#))
 - AI ([Appendix E](#))
- Complete physical examination
- Laboratory studies as outlined in Section [7.7](#)
 - Urinalysis
 - Hematology
 - Serum chemistries
- Adverse experiences
- Evidence of relapse
- Concomitant therapy
- Drug accountability

The visit procedures listed above may be completed as an unscheduled visit if the month 264 visit has already been completed.

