7.2. Premature Termination of Treatment

The reasons for premature termination of treatment follow. Teva Branded Pharmaceutical Products R&D, Inc. should be contacted before any patient is terminated from the study.

- Intolerable adverse effects.
- Patient's voluntary decision to discontinue treatment for any reason.
- Investigator's judgment that continued treatment is not in the best interest of the patient.
- Loss of patient to follow-up.
- Pregnancy.
- Gross noncompliance (i.e., use of less than 50% of prescribed doses in the preceding 3-month period).

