7.5.2. Recording and Reporting of Adverse Events

For recording of adverse events, the study period is defined for each patient as that time period from signature on the informed consent form until the last study visit.

All adverse events that occur during the defined study period must be recorded on the source documentation and transcribed to the CRF, regardless of the severity of the event or judged relationship to the study drug. For serious adverse events, the serious adverse event form must be completed and the serious adverse event must be reported immediately (see Section 7.5.5.3). The investigator does not need to actively monitor patients for adverse events once the study has ended. Serious adverse events occurring in a patient after the treatment of that patient has ended

should be reported to the sponsor if the investigator becomes aware of them, following the procedures described in see Section 7.5.5.3.

At each contact with the patient, the investigator or designee must question the patient about adverse events by asking an open-ended question such as “Have you had any unusual symptoms or medical problems since the last visit? If yes, please describe”. All reported or observed signs and symptoms will be recorded individually, except when considered manifestations of a medical condition or disease state. A precise diagnosis will be recorded whenever possible. When such a diagnosis is made, all related signs, symptoms, and any test findings will be recorded collectively as a single diagnosis on the CRF and, if it is a serious adverse event, on the serious adverse event form.

The clinical course of each adverse event will be monitored at suitable intervals until resolved, stabilized, or returned to baseline; or until the patient is referred for continued care to a health care professional; or until a determination of a cause unrelated to the study drug or study procedure is made.

The onset and end dates, duration (in case of adverse event duration of less than 24 hours), action taken regarding study drug, treatment administered, and outcome for each adverse event must be recorded on the source documentation and transcribed to the CRF.

The relationship of each adverse event to study drug and study procedures, and the severity and seriousness of each adverse event, as judged by the investigator, must be recorded as described below.

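### Section 8.1 reports adverse events only as a percent of patients treated, with no patient-year rates to support a long-term safety objective under unequal follow-up

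*Combined protocol and SAP*

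**What the plan says.** The lead-in to Section 8 names no method: "Standard reporting and analysis procedures will be employed to present the safety profile of Copaxone" is the substance of it, together with a mention of the neurologic course. Section 8.1 then plans the number and percent of patients with an adverse event, overall and by body system and term, for all patients treated. It adds that "The number of patients treated will serve as the denominator for incidence rate computation". The remaining items are summaries by maximum severity and by relationship, and displays, narratives and case report form copies for deaths and adverse-event withdrawals. Section 8.2 covers laboratory values only. No patient-year total, event rate over time or summary by period is planned.

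The first objective in Section 3 is "To assess the long-term safety of Copaxone". The same section describes the drug as "administered for up to 26 years, or until the sponsor terminates the study, on approximately 60 patients who participated in the original double-blind study". Section 7.2 lists the ways a patient may leave, including a "voluntary decision to discontinue treatment for any reason", intolerable adverse effects and loss to follow-up.

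For recording events, Section 7.5.2 says that "the study period is defined for each patient as that time period from signature on the informed consent form until the last study visit". Section 8.1 does not refer to this. Section 7.1.1 requires a further consent at month 264: "Signed informed consent for Amendment 13". Section 2.2 says that the extension should help to understand the safety and efficacy of 40 mg three times weekly against 20 mg daily in patients who switched.

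**The concern.** The percent of patients who ever had an event rises with the length of time they were watched. When everyone is followed for the same time, that does little harm. Here some patients may have contributed months and others more than two decades, and the objective is about risk over the long term. A reader who sees only the percentage cannot separate a low rate over long follow-up from a higher rate over shorter follow-up.

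The regimen question raises the same difficulty more sharply. A patient who switches late has many years on the daily regimen and few on the other. Percentages split by regimen would differ even if the event rates were identical. Without time on each regimen in the denominator, the tables planned in Section 8.1 cannot inform the comparison described in Section 2.2.

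**Working it through.** The plan gives no adverse event count, rate, dropout share or power figure, so there is no figure of its own to reproduce. The calculations below show how the planned percentage behaves. Every event rate and leaving share in them is an assumption.

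**Inputs from the documents.** Month 288 is 288/12 = 24 years on the study clock. The extension runs from month 264 to month 288, which is 2 years. About 60 patients are expected (Section 3). Onset and end dates of adverse events must be recorded (Section 7.5.2).

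**Formulas.** Let r be a constant first-event rate per year, T the length of the window and p the share of patients who leave, with leaving times spread evenly over the window and unrelated to events.
- Risk in those who stay: F = 1 − exp(−rT).
- Risk in those who leave: G = 1 − F/(rT).
- Planned percentage: (1 − p)F + pG.

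**1. One percentage, several rates (T = 24).** Setting the planned percentage to 30% and solving for r:

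| Share leaving | r per year | First events per 100 patient-years |
|---|---|---|
| 0% | 0.0149 | 1.5 |
| 25% | 0.0173 | 1.7 |
| 50% | 0.0206 | 2.1 |
| 75% | 0.0251 | 2.5 |

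Check of the last row: rT = 0.0251 × 24 = 0.602, F = 0.452, G = 1 − 0.452/0.602 = 0.249, and 0.25 × 0.452 + 0.75 × 0.249 = 0.30. The underlying rate varies by a factor of 0.0251/0.0149, about 1.7, while the reported percentage stays the same.

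**2. Months 264 to 288 alone (T = 2, r = 0.02).** F = 1 − exp(−0.04) = 3.92%. The planned percentage is 3.82% if 5% leave and 3.53% if 20% leave. The differences are 0.10 and 0.39 percentage points, or about 0.06 and 0.23 of one patient among 60. In this window the issue is close to negligible.

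**3. Time on each regimen (r = 0.02 on both, full follow-up).** A patient who switches at month 264 has 22 study years on daily injections and 2 on the other regimen: 1 − exp(−0.44) = 35.6% against 1 − exp(−0.04) = 3.9%. If the switch came at month 240, the Amendment 12 screening visit, the split is 20 and 4 years: 1 − exp(−0.40) = 33.0% against 1 − exp(−0.08) = 7.7%. The true rates are equal, so these differences come only from time. Section 8.1 plans no such split; the figures show what a split of its percentages would do.

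**4. Precision of the alternative.** With full retention, months 264 to 288 give 60 × 2 = 120 patient-years. With 20% leaving evenly they give 60 × (0.8 × 2 + 0.2 × 1) = 108. With no events, the one-sided 95% upper bound is 2.996/120 = 2.5 or 2.996/108 = 2.8 per 100 patient-years. Two events in 120 patient-years give an exact 95% interval of about 0.2 to 6.0 per 100.

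**The case against.** The strongest reply is that a percent of patients with an event is a standard and valid summary, that Section 8.1 says plainly that it tabulates number and percent of patients, and that it plans no test or threshold that a different denominator would change. All of that stands. Calling the result an incidence rate is loose wording; on its own it would not be worth raising.

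Three stronger readings are tempting, and the documents do not support them.

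- **That the planned percentage understates risk by a known amount.** Neither size nor direction is established. No event rate or dropout share is given, and Section 7.2 includes intolerable adverse effects as a reason to leave, so leaving may be related to events. The figures above assume that it is not.
- **That the protocol gives no window for adverse events.** Section 7.5.2 defines one, from consent to last visit. Amendment 13 extends the same study, Section 9.1 ties consent to entering the study, and Appendix A names the month 264 form as an extension consent. The whole-study reading is therefore the more natural one. What remains is a missing cross-reference and a missing statement of which consent starts the period.
- **That month 288 and "following 26 years of continuous Copaxone" contradict each other.** The gap is a constant two years: Section 4 pairs month 264 with 24 years of therapy, and Section 7.1 pairs the end of the extension, month 288, with 26. Patients came from an earlier double-blind study, and Section 2.1 describes those studies as designed for 24 months.

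The narratives for deaths and adverse-event withdrawals help interpretation, but they do not supply follow-up time for the other patients.

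**Conclusion.** The point holds as a gap in the planned safety summary. Section 8.1 relies on a head count alone, while the objective concerns risk over up to 26 years with unequal follow-up. Patient-year rates are a better companion to the percentages and use dates that are already required.

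If events are counted over the whole study, one percentage can fit rates that differ by a factor of about 1.7 under the assumed 0 to 75% leaving, constant rate and uninformative leaving. If they are counted over months 264 to 288 only, the effect is at most a few tenths of a percentage point in the cases examined. The regimen question depends on the adjustment more heavily, because time on each regimen is so uneven. No conclusion of the study is shown to be wrong. The documents supplied contain no more detailed analysis plan, and a later one could close the gap. Severity is minor to moderate.

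**What to change.** In Section 8.1:

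1. Keep the percentages and call them percent of patients treated.
2. Add total patient-years on treatment and event rates per 100 patient-years with 95% confidence intervals that allow for repeat events in one patient. Give them overall and by regimen at the time of the event, counting events and time over the same period.
3. Cross-refer to the study period in Section 7.5.2 and say which consent starts it.

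Cumulative incidence of first events is optional.

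No new visits or patients are needed; the work is a few sentences and some programming. Regimen is recorded at months 264 and 276 (Appendix A), so a switch between visits may have to be dated from dispensing records. Electronic case report forms begin at month 159 (Section 9.5), and the documents do not say how the earlier paper data are held, so the effort for whole-study rates is uncertain.

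Three limits should be stated with the results. Intervals will be wide, with at most about 120 patient-years in months 264 to 288. Censoring may be informative, so the rates should be read beside the planned displays for deaths and adverse-event withdrawals. Regimen is the patient's choice (Section 7.1.1), so rates by regimen remain descriptive.

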8.2. Laboratory Tests

Summary statistics (number of patients, mean, standard deviation, minimum and maximum) will be displayed for the baseline value, the last value obtained during treatment, and the change from baseline to last observed value. Frequency distributions will be presented, by test, depicting the number of patients who had “clinically significant” changes from baseline in laboratory values, defined by criteria determined by the medical monitor. Scatterplots of each continuous-type lab test will be provided illustrating the graphical relationship between the baseline and endpoint values obtained for each patient by treatment group.

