7.5. Adverse Events

7.5.1. Definition of an Adverse Event

An adverse event is any untoward medical occurrence in a patient administered a pharmaceutical product, regardless of whether it has a causal relationship with this treatment.

In this study, any adverse event occurring after the clinical study patient has signed the informed consent form should be recorded and reported as an adverse event.

An adverse event can, therefore, be any unfavorable and unintended physical sign, symptom, or laboratory parameter that develops or worsens in severity during the course of this study, or significant worsening of the disease under study, or of any concurrent disease, whether or not considered related to the study drug. A new condition or the worsening of a pre-existing condition will be considered an adverse event. Stable chronic conditions (such as arthritis) that are present before study entry and do not worsen during this study will not be considered adverse events.

Accordingly, an adverse event can include any of the following:

- intercurrent illnesses
- physical injuries
- events possibly related to concomitant medication
- significant worsening (change in nature, severity, or frequency) of the disease under study or other pre-existing conditions
- drug interactions
- events occurring during diagnostic procedures or during any washout phase of this study
- laboratory or diagnostic test abnormalities that result in the withdrawal of the patient from the study, are associated with clinical signs and symptoms or a serious adverse event, require medical treatment or further diagnostic work-up, or are considered by the investigator to be clinically significant (Note: Abnormal laboratory test results at the screening visit that preclude a patient from entering the study or receiving study treatment are not considered adverse events.)

Hospitalization due to MS exacerbation should be recorded as an adverse event only if the presentation or outcome is more severe than would normally be expected from the normal course of the disease in a particular patient.

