7.5.5. Serious Adverse Events

7.5.5.1. Definition of a Serious Adverse Event

A serious adverse event is an adverse event occurring at any dose that results in any of the following outcomes or actions:

- death
- a life-threatening adverse event (ie, the patient was at immediate risk of death from the event as it occurred); does not include an event that, had it occurred in a more severe form, might have caused death
- inpatient hospitalization or prolongation of existing hospitalization, which means that hospital inpatient admission or prolongation of hospital stay were required for treatment of an adverse event, or that they occurred as a consequence of the event

Hospitalizations scheduled before the patient signed the informed consent form will not be considered serious adverse events, unless there was worsening of the preexisting condition during the patient's participation in this study.

- Hospitalization for intravenous steroid treatment of a relapse will not be considered a serious adverse event unless it is a worsening of the condition beyond expected disease progression.
- persistent or significant disability or incapacity (refers to a substantial disruption of one's ability to conduct normal life functions)
- a congenital anomaly/birth defect
- an important medical event that may not result in death, be life-threatening, or require hospitalization, but may jeopardize the patient and may require medical intervention to prevent one of the outcomes listed in this definition
- Examples of such events are intensive treatment in an emergency room or at home for allergic bronchospasm; blood dyscrasias or convulsions that do not result in hospitalization; or the development of drug dependency or drug abuse. Note: Any suspected transmission of an infectious agent via a medicinal product is considered an important medical event.

All occurrences of possible drug-induced liver injury that meet Hy's law criteria, defined as **all** of the below, must be reported by the investigator to the sponsor as a serious adverse event:

- alanine aminotransferase (ALT) or aspartate aminotransferase (AST) elevation of >3x the upper limit of normal (ULN)
- total bilirubin elevation of >2x ULN
- absence of initial findings of cholestasis (ie, no substantial increase of alkaline phosphatase [ALP])

An adverse event that does not meet any of the criteria for seriousness listed above will be regarded as a nonserious adverse event.

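### Section 8.2 does not show each patient's worst on-treatment laboratory value, and no planned output checks the laboratory data for an unreported case of the Section 7.5.5.1 liver criterion

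*Combined protocol and SAP*

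**What the plan says.** Section 8.2 plans three laboratory displays.

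- Summary statistics are "displayed for the baseline value, the last value obtained during treatment, and the change from baseline to last observed value". The minimum and maximum among them are taken across patients at each of these points; they are not each patient's own extreme.
- For the second display, "Frequency distributions will be presented, by test, depicting the number of patients who had" changes from baseline judged clinically significant. The criteria are left to the medical monitor and are not given. No time point is named, so the table is not restricted to the last value.
- Scatterplots are planned, "illustrating the graphical relationship between the baseline and endpoint values obtained for each patient by treatment group". Endpoint is not defined; the last value is the natural reading.

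Section 7.8 requires one of four codes for every out-of-range result. For the code CS, "All clinically significant values during the study are adverse events". The code PA is for results where "Although the value is outside the normal range, the value is normal for that particular patient", and NS is for departures without clinical meaning. Section 7.5.1 makes a laboratory abnormality an adverse event on several grounds, one being that such results "are considered by the investigator to be clinically significant".

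Section 7.5.5.1 states that a case with ALT or AST above 3 times the upper limit of normal (ULN), total bilirubin above 2 times ULN and no initial sign of cholestasis "must be reported by the investigator to the sponsor as a serious adverse event". Appendix F, the reporting instruction for adverse laboratory findings, gives its own list of what makes such a finding serious: death or threat to life, permanent disability, hospital admission or a longer stay, congenital anomaly, cancer, or overdose. The liver criterion is not on it.

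**The concern.** Clinical pathology is the first-listed measure under the long-term safety objective in Section 3. Summaries of first and last values suit a drift that persists, but drug-related laboratory changes can also be transient. A value that rises at one visit and is normal at the next leaves no mark on a last-value mean or on a baseline-to-last scatterplot. Whether a reader ever sees it then depends on a judgement: the medical monitor's unstated criteria, or the site's code or adverse event report.

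The liver criterion is the clearest case. The protocol sets a numerical rule and makes reporting mandatory, yet the analysis section does not apply that rule to the data already held. If no case is reported, the planned outputs cannot separate the absence of a case from the absence of a report.

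**Working it through.** The plan gives no figure on this point to reproduce. The check compares sections and adds simple arithmetic.

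**1. Scheduled samples used by the summary and scatterplots.** Let k be the number of post-baseline scheduled samples for a completer. A last-value display uses one of them, so the share outside is (k − 1)/k.

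- Appendix A schedules laboratory tests at months 264, 276 and 288. With month 264 as baseline, k = 2 and the share outside is 1/2 = 50%. If all of the roughly 60 patients in Section 3 complete, that is 60 × 1 = 60 of 60 × 2 = 120 results per test, and fewer with dropout.
- Section 7.4 speaks of tests every 6 months. On that reading k = 24/6 = 4 and the share is 3/4 = 75%. The visit checklists and Appendix A do not schedule the extra samples.
- Section 8.2 does not say which visit is baseline. An earlier baseline makes the share larger.

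**2. Other routes for an intermediate value.**

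| Route | Condition |
|---|---|
| By-test table, Section 8.2 | Meets the medical monitor's criteria, which are not stated |
| Adverse event through Section 7.8 | Coded CS; a valid result coded NS or PA does not qualify by this route |
| Adverse event through Section 7.5.1 | Led to withdrawal, symptoms, treatment or more investigation, or the investigator judged it important |

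Each route works, but each passes through a judgement or a clinical consequence. None displays the patient's lowest or highest value.

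**3. The joint liver case.**

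- If reported: Section 7.5.2 has the findings entered as one diagnosis when a diagnosis is made, and Section 8.1 tabulates patients by event term, severity and relationship. The case can appear there as a liver diagnosis. Narratives are planned only for deaths and withdrawals due to adverse events.
- If not reported: the by-test rows of Section 8.2 remain. With a patients in the ALT/AST row and b in the bilirubin row out of 60, the number in both lies between max(0, a + b − 60) and min(a, b). With a = b = 1 that is 0 to 1, so these rows alone do not settle it. This assumes that the medical monitor's criteria flag both components.
- A patient with no symptoms and no admission meets Section 7.5.5.1 but no item on the Appendix F list. A site working from that list could miss the case.
- Under Section 10.5 the medical monitor reviews serious adverse events, so that review follows a report.

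**4. What a liver check can deliver.** If it finds no case in 60 patients, the exact one-sided 95% upper limit is 1 − 0.05^(1/60) = 4.9%. If only 40 patients continue (an assumption), it is 1 − 0.05^(1/40) = 7.2%. The check makes a zero trustworthy; it does not make it precise.

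**5. The drawback of worst-value tables.** They flag more patients as samples accumulate. Take an independent chance p of an isolated abnormal result per sample, with p from 1% to 5% (an assumption). Over two samples, 1 − (1 − p)² runs from 1 − 0.99² = 2.0% to 1 − 0.95² = 9.8%, against 1.0% to 5.0% at the last value.

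**The case against.** The strongest reply is that the plan has several safeguards and that this is a descriptive extension in about 60 long-term patients. Much of that stands.

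- The by-test table can count a significant change at any visit. A reader might infer that results before the last sample drop out of the analysis. The documents do not support that: such results are outside two of the three displays only.
- A reader might also infer that no planned output can show a joint liver case, or that the tables would look the same with and without one. Neither follows. A reported case is a mandatory serious adverse event and can enter Section 8.1 as a single diagnosis, so the outputs would differ. The gap concerns an unreported case.
- Site recognition is not the only control. Every out-of-range result must be coded, original laboratory reports are open to monitors (Section 9.5), sites are monitored for data recording and adherence (Section 9.6.2), and the sponsor evaluates each reported serious event (Section 7.5.5.3.1). A result above 3 times ULN coded NS or PA would be a misclassification, and nothing suggests that it is common.
- Appendix F does not override Section 7.5.5.1, and it still requires every adverse laboratory finding to be recorded.

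What the reply does not remove: coding and site monitoring are procedures, not analyses. No planned output shows the worst value independently of coding or unstated criteria, and none compares the liver criterion with the laboratory data. The Appendix F omission is in the text.

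**Conclusion.** The point holds as a gap in specification, minor to moderate in weight. A transient abnormality can reach the reader only through a table with unstated criteria or through the site's coding or reporting. An unreported joint liver case is not cross-checked, and one of the protocol's two lists of serious laboratory events leaves the criterion out.

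The size is 1 of 2 post-baseline scheduled samples per completer outside the summary and scatterplots. It rests on month 264 as baseline, on the Appendix A schedule, and on reading endpoint as last value. It describes what two displays leave out and does not count lost signals. Nothing in the documents shows that a case was missed, and the weight is limited because the plan is descriptive, the data are kept and other routes exist.

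**What to change.** 1. **Section 8.2.** Keep the planned displays. For months 264 to 288, add a low/normal/high shift table for each test from baseline to worst on-treatment value, with lowest and highest separate and unscheduled samples included. Put it beside the same table to last value, with a note that worst-value counts rise with the number of samples. State which visit is baseline, what endpoint means, and the medical monitor's criteria, and say that these criteria apply to any on-treatment value.
2. **Liver listing.** From the laboratory data, list every patient with any on-treatment ALT or AST above 3 times ULN and any on-treatment total bilirubin above 2 times ULN. Show the date of each and ALP as a multiple of ULN. Do not require the same date, since Section 7.5.5.1 does not. Have the no-cholestasis limb judged medically, because the protocol gives no ALP cut-off. Reconcile each case with the serious adverse event reports.
3. **Appendix F.** Add the Section 7.5.5.1 liver criterion to the list of serious laboratory events.

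The cost is wording, a few tables and one reconciliation, with no new visits or samples. Reference ranges must be carried in the data set. Electronic case report forms cover visits from month 159 (Section 9.5), so months 264 to 288 fall within the electronic period. Section 7.8.3 lists bilirubin without saying total; confirm this before the listing is programmed.
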